2.1 Exclusion criteria

Participants will be excluded from analyses for any of the following reasons:

- Not a resident of England
- Unable to link dietary and lifestyle data with hospital episode data (e.g. no NHS number provided and unable to match with records)
- Unreliable or missing nutrient or covariate data (e.g., $\geq 20\%$ of food frequencies missing)
- Had a hip fracture or osteoporosis before or on the date of recruitment

3. Exposures

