To explore potential associations between foods and beverages and hip fracture incidence, food and beverage intake variables in grams per day will be calculated by multiplying servings per day intake variables by standard portion weights, and summing relevant FFQ items. Food and beverage intake variables (grams/day) will be used to explore the effects of increment increases in intake on hip fracture risk, and to categorise participants into non-consumers (if > 1000 participants in this category) and levels of intake for all exposure variables, ensuring equal distribution of the population size among categories where possible. For intakes of milk, tea, coffee, and tea and coffee combined, increment increases and categories of intake will be defined by glasses and cups per day using standard sizes with the lowest exposure category as the reference group. For fruits, vegetables, and fruits and vegetables combined, categories will be defined to compare intakes below and above the

recommended five-a-day (400 g/day) intake, which will be used as the reference category. All other food and beverage exposures will be split into thirds or quarters.

Nutrient variables will be derived by multiplying food and beverage intakes (g/day) by nutrient concentrations in each food or beverage item using McCance and Widdowson’s Food Composition database (5th edition) [2].

4. Outcomes

Participants will be followed up via record linkage to the NHS Hospital Episode Statistics up to 31 March 2019. The primary outcome will be hip fracture incidence (International Classification of Diseases, ICD-9 code 820, and ICD-10 codes S72-S72.2). Hip fracture cases will also be identified by hip replacements (ICD-10 code Z96.64). The timeframe will be person years until hip fracture incidence (or until end of study period or death in those without a hip fracture), calculated as age at time of event (or non-event) minus age at study entry.

5. Sample size

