The minimum detectable hazard ratio for the potential association between each primary exposure and hip fracture was estimated assuming a sample size of 26,300 (after applying exclusion criteria), an overall probability of hip fracture incidence of 3%, $p < 0.05$, and 80% power. For the dietary group analysis, a theoretical standard deviation of the exposure was calculated based on the percentage of participants in each category (Table 2). The minimum detectable effect of other primary exposures was calculated per standard portion size increase in intake using standard deviations of each exposure from the data in hand. Standard portion sizes were estimated from the Foods Standards Agency and previous UKWCS analyses [3, 4]. A standard portion size for total animal products was calculated by averaging standard servings of meat, fish, eggs, and dairy products.

Table 2: Minimal detectable hazard ratios for associations between primary exposures and hip fracture risk.

Exposure	SD	Minimum detectable HR
Dietary group (vegetarians vs non-vegetarians)	0.36	1.32
Fruit and vegetables (per 80 g increase)	300 g	0.98
Fruits (per 80 g increase)	227 g	0.97
Vegetables (per 80 g increase)	139 g	0.95
Total animal products (per 120 g increase)	248 g	0.95
Total meat (per 150 g increase)	81.2 g	0.84
Total fish (per 140 g increase)	28.3 g	0.61
Eggs (per 88 g increase)	18.6 g	0.63
Total dairy (per 105 g increase)	214 g	0.95

Tea and coffee (per cup increase)	2.17 cups	0.96
Tea (per cup increase)	2.01 cups	0.95
Coffee (per cup increase)	1.65 cups	1.06
Protein (per 25 g increase)	26.3 g	0.91
Calcium (per 300 mg increase)	365 mg	0.91
Vitamin D (per μg increase)	1.67 μg	0.94

1 cup of tea or coffee = 260 ml. SD = Standard deviation. HR = Hazard ratio. The SD for dietary group is theoretical and has arbitrary units.

6. Descriptive statistics

Baseline socio-demographic, anthropometric, diet, and lifestyle characteristics of the cohort were collected via questionnaire at baseline, and will be summarised (e.g. presenting their means and standard deviations) by: 1) dietary group (both for data-derived and self-identified dietary group); 2) total fruit and vegetable consumption; 3) total animal product consumption; 4) total tea and coffee consumption, and 5) protein, calcium, and vitamin D intakes, to report any differences in covariates (including co-exposures) between groups at baseline.

7. Statistical modelling

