To estimate the population impact of diet on hip fracture incidence, we will determine the absolute risk difference for hip fracture between dietary groups and categories of exposure intakes, respectively. Predicted incidences and absolute risk differences will be calculated per 1000 person years and per 1000 people over 10 years using hazard ratios and 95% confidence intervals expressed as floating absolute risks [10].

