7.3 Sensitivity analyses

For the dietary group analysis, we will present models with vegans and vegetarians separated. We will also compare risk estimates between self-identified and data-derived dietary groups. For all analyses, we will explore the potential mediating effect of covariates identified in DAG models as being associated with hip fracture incidence and plausibly caused by the exposure by adding each of these covariates to adjusted models independently. Models will be presented with and without adjustment for BMI. To reduce risk of bias due to changes in exposure over time, phase two dietary data (collected four years after baseline) will be compared with baseline dietary data. In cases of substantial exposure change over time (e.g., > 10% of participants changing their dietary group or primary exposure categories), models will be repeated using phase two data if there is sufficient power.

Additional sensitivity analyses will involve excluding cases occurring in the first five years of follow-up (to check for reverse causality), and excluding participants on long-term treatment for illnesses. All analyses will be performed using Stata. Two-sided p values < 0.05 will be considered statistically significant. We acknowledge that the large number of planned exposure-outcome association tests increases the risk of a type-2 error. However, the alpha value will not be restricted below $p < 0.05$ since secondary analyses (including most nutrient-hip fracture associations) will be exploratory, with only the primary analyses considered hypothesis-testing. All analyses performed and effect sizes computed will be presented in resulting manuscripts to avoid bias in selection of the reported result.

8. Missing data

Participants with missing data for an FFQ item will be considered non-consumers. Participants will be excluded from each specific analysis if they have missing data for any other variable required in that analysis. Techniques to impute missing dietary or covariate data will not be performed.

9. Timescales

Target analysis completion date (excluding manuscript preparations): Jan 2021.

10. References

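### Section 4 gives no end of follow-up for women who leave hospital-record coverage, so unobservable time counts as fracture-free and the absolute rates come out somewhat low (minor)

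*SAP*

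**What the plan says.** Section 4 names one source of outcomes: "Participants will be followed up via record linkage to the NHS Hospital Episode Statistics up to 31 March 2019". It then sets the time at risk: "The timeframe will be person years until hip fracture incidence (or until end of study period or death in those without a hip fracture", which is "calculated as age at time of event (or non-event) minus age at study entry". Without a fracture, follow-up therefore ends in only two ways: death or the end of the study.

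Section 2.1 lists two exclusions that bear on coverage: "Not a resident of England" and "Unable to link dietary and lifestyle data with hospital episode data (e.g. no NHS number provided and unable to match with records". Both remove a woman from the analysis altogether; neither ends her person-time part-way. The residency item has no date, whereas the prior-fracture item in the same list is tied to recruitment.

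Section 8 covers missing variables only: "Participants will be excluded from each specific analysis if they have missing data for any other variable required in that analysis". The sensitivity analyses in section 7.3 do not mention loss of coverage.

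The person-years feed directly into results. The last paragraph of section 7.1.1 states: "Predicted incidences and absolute risk differences will be calculated per 1000 person years and per 1000 people over 10 years".

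**The concern.** A woman can be resident and linked at entry and later move out of reach of the hospital records. From then on a hip fracture cannot appear in her record, yet section 4 keeps her in the risk set as fracture-free. Her later years enter the denominator of every rate and can add nothing to the numerator.

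The absolute rates are at stake first. They are biased downward even if leaving has nothing to do with diet. The loss also builds up with follow-up, so it falls more heavily on later years, when the women are older. Hazard ratios are at stake only if leaving differs between the diet groups being compared, given the covariates in the model.

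**Working it through.** **Text check.** Sections 2.1, 4, 7.1.1, 7.3 and 8 were set side by side. None ends person-time at a move, at emigration or at loss of linkage. Section 4 therefore stands as a closed list.

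**The plan's own figure.** Section 5 gives the size as "assuming a sample size of 26,300 (after applying exclusion criteria" and a 3% probability of fracture, so events = 26,300 × 0.03 = 789. For dietary group (SD 0.36, two-sided 0.05, 80% power), the minimum detectable HR is exp[(1.960 + 0.842) / (0.36 × √789)] = exp(2.802 / 10.11) = 1.319, against 1.32 in Table 2. It reproduces. The implied standard error of the log HR is 1 / 10.11 = 0.099.

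**Assumptions, none of them in the SAP.** Follow-up is 20 years, deaths are ignored, and exits are spread evenly over that time. A share q of women leaves. The hazard is either flat or doubles every 6 years (k = ln 2 / 6 = 0.1155).

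**Share m of a leaver's events that is missed.** With even exit, a leaver has gone by time t with probability t/20, so m is the hazard-weighted mean of t divided by 20.
- Flat hazard: m = 10 / 20 = 0.50.
- Rising hazard: mean t = 20 × 10.08 / 9.08 − 1 / 0.1155 = 13.55, so m = 0.677.

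**Incidence deficit = q × m.**

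| q | flat | rising |
|---|---|---|
| 2% | 1.0% | 1.4% |
| 10% | 5.0% | 6.8% |

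For scale, 789 events over 26,300 × 20 = 526,000 person-years is 1.50 per 1000. The extremes of the table would show this as 1.485 (× 0.990) and 1.40 (× 0.932).

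**First 10 years only.** The same method gives m = 5 / 20 = 0.25 (flat). With a rising hazard, mean t is 10 × 3.175 / 2.175 − 8.66 = 5.94, so m = 0.297. The deficit runs from 0.02 × 0.25 = 0.5% to 0.10 × 0.297 = 3.0%.

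**A second exit model.** A constant exit rate e over T years gives unobservable person-time of 1 − (1 − exp(−eT)) / (eT). For e of 0.05% to 0.5% per year and T of 15 to 25 years this is 0.4% to 6.0%. Missed fractures are 0.4% to 6.0% with a flat hazard and 0.5% to 8.2% with a hazard rising 10% per year. The order of size is the same.

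**Hazard ratio, crude two-group case.** Factor = (1 − q₁m) / (1 − q₀m).
- Equal exit: 1, so no bias.
- 2% against 6%: 0.97 / 0.99 = 0.980 (flat), 0.973 (rising).
- 5% against 10%: 0.95 / 0.975 = 0.974 (flat), 0.965 (rising).

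On the dietary-group contrast, |ln 0.980| / 0.099 = 0.20 and |ln 0.965| / 0.099 = 0.36. Even these assumed differences shift the estimate by 0.2 to 0.4 of a standard error.

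**The case against.** **Coverage is inferred.** The SAP does not say that the hospital data cover England only. That follows from a residency exclusion placed beside a linkage exclusion, with one outcome source. The inference is natural but should be confirmed. It also cannot be said that residency was judged once, at recruitment: the item is undated. Even a later date would drop women rather than stop their clock.

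**Other documents may cover it.** The protocol or the cited cohort profile may describe tracing. This stands only in part, because section 4 does not leave the matter open. It states a rule, and an analyst who follows that rule will count the unobservable time.

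**Hazard ratios.** A reader might infer that the diet hazard ratios are biased because leaving depends on education, occupation or ethnicity. The document does not support that as it stands. Section 7.1.1 lists ethnicity, socio-economic status and education as likely confounders, and Supplementary Table 2 derives socio-economic status from occupation. If exit depends on diet only through these, it is roughly equal across diets within covariate levels, and the factor is close to 1. The crude factors above apply only to a difference that remains after adjustment, and nothing in the SAP points to one.

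**Table 2.** A reader might also set a factor of 0.97 beside the detectable HRs of 0.94 to 0.98 in Table 2 and conclude that bias and effect are of equal size. That is not like for like. Those rows are per portion, cup or microgram, whereas the factor compares two groups. The only two-group row is 1.32.

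**Conclusion.** The point holds and is minor. As written, section 4 counts time in which no fracture can be recorded as fracture-free time, which lowers the absolute rates of section 7.1.1. Under assumed exit of 2% to 10% over 20 years, incidence is too low by about 1% to 7%, and 10-year risk by about 0.5% to 3%. The upper ends need both 10% leaving and the steep hazard. Exit rates, follow-up length and hazard shape are all assumptions, so no single corrected figure can be given.

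The hazard ratios are unaffected if exit is equal across diets after adjustment, and probably little affected otherwise. The sample-size figures in section 5 are not called into question.

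**What to change.** In section 4, end person-time at the earliest of hip fracture, death, recorded exit from England or loss of NHS registration, and 31 March 2019. Name the source of the exit date. In section 2.1, state the date at which the residency exclusion applies. If another study document already has such a rule, cite it and bring section 4 into line.

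If no exit date is held, report the absolute rates with that limitation and a short sensitivity calculation over assumed exit rates, of the kind shown above.

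The cost is one or two sentences, the exit date where it is held, and slightly less person-time. Censoring removes the unobservable time but does not recover the missed fractures. With a rising hazard, a crude rate will still be weighted toward earlier years: at 10% leaving, (1 − 0.068) / (1 − 0.05) = 0.981 of the full-follow-up rate.

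Stopping all follow-up at 10 years may look like a simple substitute, but it costs too much. Under the rising hazard it keeps 2.175 / 9.08 = 24% of events, about 189 of 789, and the detectable dietary-group HR moves from 1.32 to exp[2.802 / (0.36 × √189)] = 1.76. With a flat hazard it moves to about 1.48. Such an analysis could not show a shift of a few per cent.

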7.1 Main analyses

We will fit Cox proportional hazard regression models to estimate the hazard ratios (HR) and 95% confidence intervals (95% CI) for associations between 1) the dietary groups and hip fracture incidence, with regular meat-eaters as the reference group; and 2) between intake of: fruits, vegetables, fruits and vegetables combined, total animal products, meat, fish, dairy, eggs, tea, coffee, tea and coffee combined, total protein, calcium, and vitamin D and hip fracture incidence. Each primary food, beverage, and nutrient exposure variable will be modelled as both categorical and continuous so that models can be fit comparing the risk of hip fracture between categories of intakes (where the target estimand is the relative causal effect of the exposure on hip fracture risk) and per increment increase in exposure intake (where the target estimand is the total causal effect of the exposure on hip fracture risk). We will also assess HR's for hip fracture as a function of primary exposure intake (non-linear dose-response) via restricted cubic splines for intake of: fruits, vegetables, fruits and vegetables combined, tea, coffee, and tea and coffee combined, since previous studies have shown non-linear relationships between each of these variables and hip fracture risk [5, 6]. Proportional hazards assumptions will be assessed based on Schoenfeld residuals.

7.1.1 Accounting for confounding

For all primary analyses, we will present age-adjusted, minimally adjusted, and fully adjusted models. Minimally adjusted models will be adjusted for the minimally sufficient set of confounders. Three directed acyclic graphs (DAGs) will be constructed using the online tool DAGitty, and following

available guidelines on the creation and reporting of DAG models to determine minimal adjustment sets in models of associations between hip fracture and 1) dietary patterns; 2) foods and beverages; and 3) nutrient intakes [7]. Confounders will be considered as covariates that are 1) risk factors of the outcome; 2) associated with the exposure; and 3) not caused by the exposure [8]. Confounders common to all research questions will likely include: age at baseline, ethnicity, socio-economic status, education, marriage, physical activity, smoking, alcohol, BMI (or height and weight), number of children, menopausal status, chronic disease at baseline, and fracture at baseline (non-hip). A list of likely confounders and their derivation is summarised in Supplementary Table 2. We will adjust for baseline chronic disease and fracture prevalence at sites besides the hip rather than excluding these subjects in minimally adjusted models to reduce the risk of selection bias that would result from excluding unhealthier subjects. Fully adjusted models will be further adjusted for competing exposures.

Energy intake will be adjusted for using the ‘all-components’ method for all analyses except dietary groups, for which energy intake could plausibly be a mediator, thus will remain unadjusted [9]. This method involves adjusting for all other individual components of energy intake besides the exposure at hand, and has been shown to produce the least biased and most precise estimand for relative and total causal effects [9]. For food and beverage exposures of interest, this will involve mutual adjustment for other major foods and beverages or food and beverage groups that might be associated with hip fracture incidence. For energy-contributing nutrient exposures of interest (macronutrients), this will involve mutual adjustment for other energy-contributing nutrients (e.g., saturated and unsaturated fat). For non-energy contributing nutrient exposures (micronutrients), this will involve adjustment for all energy-contributing nutrients, whilst avoiding over-adjustment as a result of high correlation between nutrients.

To estimate the population impact of diet on hip fracture incidence, we will determine the absolute risk difference for hip fracture between dietary groups and categories of exposure intakes, respectively. Predicted incidences and absolute risk differences will be calculated per 1000 person years and per 1000 people over 10 years using hazard ratios and 95% confidence intervals expressed as floating absolute risks [10].

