Tea and coffee (con)	Sum tea (con) and coffee (con) to give servings/day of tea and coffee combined
4. Nutrients	
Energy (con)	Multiply intake of each item on the FFQ (grams/day) by the energy content of that item (kcal), and sum
Total protein (cat)	Categorise total protein (con) into non-consumers and quartiles of intake
Total protein (con)	Multiply intake of each item on the FFQ (grams/day) by the protein content of that item, and sum to give protein (g/day)
Animal protein (con)	Multiply intake of each item on the FFQ (grams/day) by the animal protein content of that item, and sum
Vegetable protein (con)	Multiply intake of each item on the FFQ (grams/day) by the vegetable protein content of that item, and sum
Animal : vegetable protein ratio (con)	Divide animal protein (g/day) by vegetable protein (g/day)
Dairy protein (con)	Multiply intake of each item on the FFQ (grams/day) by the dairy protein content of that item, and sum
Non-dairy animal protein (con)	Animal protein (con) – dairy protein (con)

Soy protein (con)	Multiply intake of each item on the FFQ (grams/day) by the soy protein content of that item, and sum
Non-soy vegetable protein (con)	Vegetable protein (con) – soy protein (con)
Fibre (con)	Multiply intake of each item on the FFQ (grams/day) by the fibre content of that item, and sum
Fat (con)	Multiply intake of each item on the FFQ (grams/day) by the fat content of that item, and sum
SFA (con)	Multiply intake of each item on the FFQ (grams/day) by the saturated fat content of that item, and sum
MUFA (con)	Multiply intake of each item on the FFQ (grams/day) by the monounsaturated fat content of that item, and sum
PUFA (con)	Multiply intake of each item on the FFQ (grams/day) by the polyunsaturated fat content of that item, and sum
Heme iron (con)	Multiply intake of each item on the FFQ (grams/day) by the heme iron content of that item, and sum
Non-heme iron (con)	Multiply intake of each item on the FFQ (grams/day) by the non-heme content of that item, and sum
Calcium (con)	Multiply intake of each item on the FFQ (grams/day) by the calcium content of that item, and sum
Folate (con)	Multiply intake of each item on the FFQ (grams/day) by the folate content of that item, and sum
Sodium (con)	Multiply intake of each item on the FFQ (grams/day) by the sodium content of that item, and sum
Vitamin B1 (con)	Multiply intake of each item on the FFQ (grams/day) by the vitamin B1 content of that item, and sum

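### The SAP's 'all-components' energy adjustment is implemented for foods and beverages with a partial, unfixed set of components, so some energy sources may be left out of those models

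*SAP*

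**What the plan says.** Section 7.1.1 of the SAP sets the scope: "Energy intake will be adjusted for using the ‘all-components’ method for all analyses except dietary groups". It defines the method as "adjusting for all other individual components of energy intake besides the exposure at hand", and justifies the choice by saying that it "has been shown to produce the least biased and most precise estimand for relative and total causal effects".

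The section then implements the method separately for three kinds of exposure:

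- **Foods and beverages:** "mutual adjustment for other major foods and beverages or food and beverage groups that might be associated with hip fracture incidence".
- **Macronutrients:** mutual adjustment for the other nutrients that contribute energy, with no condition about hip fracture.
- **Micronutrients:** "this will involve adjustment for all energy-contributing nutrients, whilst avoiding over-adjustment as a result of high correlation between nutrients".

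Section 7.1 names two estimands: a relative causal effect for models with categorised intake, and a total causal effect for models per increment of intake.

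Supplementary Table 1 derives a total energy variable: "Multiply intake of each item on the FFQ (grams/day) by the energy content of that item (kcal), and sum". Section 2 uses energy intake to exclude implausible records (below 500 or above 5000 kcal/day). No model specification assigns the variable to a model.

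**The concern.** The definition covers every other component of energy intake, but the food and beverage implementation covers a selection. Energy from foods outside the selection is then free to vary with the exposure. Three things are at stake.

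- **The justification.** The SAP relies on a property stated for the full method. Nothing in the SAP shows that it survives when only part of energy intake is adjusted for.
- **The relative-effect estimand.** A relative effect compares the exposure with whatever is eaten in its place. If some energy sources are outside the model, that comparator is not defined, whether or not those foods affect fracture themselves.
- **Residual confounding.** Leaving out a food because it has no effect of its own on fracture is safe only if it is not also a marker of a shared cause. The total amount eaten, and over- or under-reporting on the FFQ, tend to move all items together. Foods left out of the model can therefore carry information that would have reduced confounding. For tea and coffee, which presumably supply little energy themselves, almost all energy would have to be covered by the adjustment set.

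The point concerns the food and beverage models in sections 7.1 and 7.2.2. The dietary-group models are deliberately left unadjusted for energy, and the nutrient models are described more completely.

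**Working it through.** **1. Reading the clause.** The phrase about possible association with hip fracture can qualify the whole list or only the food and beverage groups.

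- If it qualifies the whole list, the set is limited to items believed to bear on the outcome.
- If it qualifies only the groups, the set is still limited to major foods and beverages, which are not listed.

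Both readings give less than all components.

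**2. Looking for the missing part elsewhere in the SAP.**

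- The food sections of Supplementary Table 1 cover fruits and vegetables, animal products, and tea and coffee. There is no group for bread and cereals, potatoes, pulses, nuts, fats, sugars or confectionery. The table lists exposures, so further groups could still be built, but the SAP does not say that they will be.
- Supplementary Table 2 contributes alcohol and no other dietary covariate.
- Total energy is derived, but no model is said to contain it.

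No section restores the full set.

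**3. Does the sample size section bear on this?** No. Table 2 reproduces approximately from exp(±(1.96 + 0.84) / (√(26,300 × 0.03) × SD/increment)): dietary group 1.319 against 1.32, fish 0.611 against 0.61, protein 0.910 against 0.91. The largest gap is calcium, 0.921 against 0.91. Energy adjustment is not an input.

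**4. Illustration with a shared cause (assumed model; the SAP gives no figures for this).** Take 12 standardised components X_i = λU + e_i, where U is a shared cause that drives the outcome with coefficient 1, and X_1 has no effect of its own. With k of the 12 in the model, the coefficient on X_1, which is pure bias, is

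λ / (1 − λ² + kλ²).

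- λ² = 0.2, k = 6: 0.447/2.0 = 0.224. All 12: 0.447/3.2 = 0.140. Reduction 1 − 2.0/3.2 = 38%.
- Smallest, λ² = 0.1, k = 8: 1 − 1.7/2.1 = 19%.
- Largest, λ² = 0.3, k = 4: 1 − 1.9/4.3 = 56%.

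Because these components are exchangeable, adding the sum of those left out gives exactly the result of the full model.

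**5. How far that depends on the assumptions.**

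- *More components already in the model.* k = 11, λ² = 0.1: 1 − 2.0/2.1 = 5%. k = 10, λ² = 0.3: 1 − 3.7/4.3 = 14%.
- *Part of U already captured by other covariates.* If they explain a share R² of U, write v = 1 − R²; the bias becomes λv / (1 − λ² + kλ²v). With R² = 0.7, λ² = 0.2, k = 6: 0.134/1.16 = 0.116, against 0.134/1.52 = 0.088 for all 12, a reduction of 24%. With λ² = 0.1, k = 8: 1 − 1.14/1.26 = 10%.
- *Bias that remains in the full model.* From 0.548/4.3 = 0.127 (λ² = 0.3) to 0.316/2.1 = 0.151 (λ² = 0.1). Completing the set reduces this bias but does not remove it.

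**6. Illustration on the hazard-ratio scale (also assumed).** Take one adjusted and one omitted component, equal pairwise correlation ρ, and no shared cause. The exposure HR per SD is multiplied by exp(g × ln HR_omitted), with g = ρ/(1 + ρ). For ρ from 0.1 to 0.4, g runs from 0.091 to 0.286.

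| HR per SD of omitted component | Factor on exposure HR per SD |
|---|---|
| 1.00 | 1.00 |
| 0.95 | 0.995 to 0.985 |
| 0.90 | 0.990 to 0.970 |
| 0.80 | 0.980 to 0.938 |

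Table 2 is per portion, so the scales differ. For vegetables a portion is 80/139 = 0.576 SD: a factor of 0.985 becomes 0.985^0.576 = 0.991, and 0.938 becomes 0.964, beside a stated minimum detectable HR of 0.95.

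**The case against.** The strongest reply is that much of the feared confounding is already addressed. Section 7.1.1 lists BMI (or height and weight), physical activity and alcohol as likely confounders, and the fully adjusted models add competing exposures. The final covariates could therefore turn out nearly complete. The sponsor could add that, under its own definition of a confounder, a food unrelated to fracture need not be adjusted for.

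Much of this stands, and it rules out several stronger conclusions that a reader might draw:

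- *That adjustment is made only for foods thought to be linked to hip fracture.* This is one parse of the sentence; on the other, major foods enter without that condition.
- *That the models lack the cited property.* The claim rests on a cited source, and the SAP does not show how far the property survives partial adjustment. All that can be said is that it does not automatically carry over.
- *That all primary food and beverage hazard ratios are confounded, or biased by 19% to 56%.* Those percentages are relative reductions in an assumed model with exchangeable components, a wholly unadjusted shared cause, and a k that was chosen and not taken from the SAP. Real foods are not exchangeable, so the exact match between a remainder term and the full model is not a general result.

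What the reply does not answer is the mismatch itself. Physical activity enters as two categories based on sweat-inducing exercise, and weight and height are self-reported. No planned covariate captures FFQ reporting, and the energy limits in section 2 trim only the extremes. The relative-effect estimand needs its comparator fixed even if the omitted foods have no effect on fracture.

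**Conclusion.** The point holds as an internal inconsistency with an unfixed adjustment set. Section 7.1.1 names and justifies a method that covers all energy components, then specifies a partial and unlisted set for food and beverage exposures. Some energy sources may be left unadjusted. The substitution contrast is then undefined, and there may be residual confounding by total intake and reporting beyond what the BMI and physical activity terms remove.

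The size cannot be determined from the SAP. It could be nil for the total effect if the omitted foods have no effect on fracture and carry no information on a shared cause, and small if the final covariates are nearly complete. The illustrations show the direction of the benefit and how strongly it depends on assumptions; they do not estimate bias in this cohort. The case for change rests on matching the models to the named method at low cost.

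**What to change.** In every food and beverage model that adjusts for energy (categorical, continuous and spline), add one covariate: remaining energy, in kcal/day, from all FFQ items that are neither the exposure nor an already adjusted food. Keep the planned mutual adjustments, and list the adjusted foods for each exposure so that the remainder is defined. If adjusted foods enter in grams, the terms will not literally sum to total kcal, but every energy source will be covered.

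The variable comes from the item-level energy already calculated for the total energy variable in Supplementary Table 1, so no new data are needed. The cost is one extra parameter per model and possibly slightly wider intervals if it is collinear with the adjusted foods.

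If the sponsor prefers the partial set, the SAP should stop calling it 'all-components' and drop the claim attached to that method.
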